3.1.1 Randomization

492

Participants who were assigned to the CLC group in the original RCT will be randomly assigned to one of two treatment groups in a 1:1 ratio:

494

1. CLC Group

495

2. PLGS Group

496

The participant's randomization group assignment is determined by completing a Randomization case report form on the study website. The randomization list will use a permuted block design, stratified by clinical center.

499

The participant will be included in the data analysis regardless of whether or not the protocol for the assigned randomization group is followed. Thus, the investigator must not randomize a participant until he/she is convinced that the participant/parent will accept assignment to either of the two groups.

503

It was decided that it was more important to stratify randomization by site than by factors such as baseline time in range, HbA1c, or device use since these factors will be easier to adjust for in analysis than will site in view of the relatively small number at each site.

506

3.2 Training for the Group Switching from SAP in the Original RCT to CLC (Control-IQ System)

508

Participants who were assigned to the SAP group in the original RCT will use CLC during the extension study. These participants will receive study system training on the Control-IQ system. This training sessions can occur on the same day or extend to up to one additional day if needed within 1-7 days from assignment; participants will not take the study system home until training has been completed.

513

For participants <18 years old, the parent/guardian will be trained on severe hypoglycemia emergency procedures including removal of the study pump and administration of glucagon. The parent/guardian will be asked to attend any/all of the other training procedures.

516 **3.2.1 Control-IQ System Training Details**

517 Participants will receive system training by a qualified trainer. The study system includes the
518 Tandem t:slim X2 with Control-IQ technology and associated Dexcom G6 CGM.

519 CGM training may include any of the following refresher topics as needed:

- 520 • The participant will be instructed and supervised on how to insert the sensor and transmitter.
521 • The participant will learn how to calibrate the CGM unit
522 • The participant will learn how to access the CGM trace via the t:slim X2 with Control-IQ
523 user interface
524 • Participants will be asked to perform fingerstick blood glucose measurements in accordance

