- 1279 • System Usability Scale (SUS)
- 1280 • Technology Acceptance Survey
- 1281 • Control-IQ Patient-Reported Outcomes Questionnaire
- 1282

1283 Other

- 1284 • Insulin
 - 1285 ◆ Total daily insulin (units/kg)
 - 1286 ◆ Basal: bolus insulin ratio
- 1287 • Weight and Body Mass Index (BMI)
- 1288

1289 **8.4 Objective 1 Analyses**1290 **8.4.1 Principles of Analyses**

1291 All analyses comparing the CLC arm with PLGS arm will follow the intention-to-treat (ITT)
1292 principle with each participant analyzed according to the treatment assigned by randomization.
1293 Safety outcomes will be reported for all enrolled participants.

1294 If more than 5% of participants have fewer than 50% of post-randomization CGM data,
1295 the analyses will be replicated excluding such participants. In addition, analyses will be
1296 replicated including only those participants from the CLC and PLGS groups who used the
1297 system for >80% overall.

1298 The analyses described below include a pre-specified list of covariates. As an additional
1299 sensitivity analysis, any baseline demographic or clinical characteristics observed to be
1300 imbalanced between treatment groups will be added as covariates to the analyses. The
1301 determination of a meaningful baseline imbalance will be based on clinical judgement and not a
1302 p-value.

1303 With respect to missing data, it is worth emphasizing that any statistical method for handling
1304 missing data makes a number of untestable assumptions. The goal will be to minimize the
1305 amount of missing data in this study so that results and conclusions will not be sensitive to which
1306 statistical method is used. To that end, sensitivity analyses will be performed to explore whether
1307 results are similar for when using different methods. The following methods will be applied:

- 1308 • Direct likelihood (analysis described below)
- 1309 • Rubin's multiple imputation
- 1310 • Available cases only

1311

1312 **8.4.2 Analytic Methods**1313 CGM Metrics

1314 Summary statistics (mean \pm SD or median (quartiles)) will be reported for each CGM metric and
1315 for differences from pre-randomization by treatment group.

1316 The analyses will be done using direct likelihood. A longitudinal linear regression model will be
1317 fit with the metric at baseline and follow-up as the dependent variable. This model will adjust for
1318 age as fixed effect and site as a random effect. The analyses will report the point estimate, 95%

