1319 confidence interval and p-value for the treatment group difference at follow-up. Residual values
1320 will be examined for an approximate normal distribution. If residuals are highly skewed, then a
1321 transformation or robust statistical method (e.g., non-parametric or MM estimation) will be used
1322 instead.

1323 HbA1c

1324 Summary statistics (mean \pm SD or n(%)) will be reported for the central lab HbA1c (continuous
1325 variable) at 13-weeks and for differences from randomization by treatment group. A longitudinal

1326 model will be fit using values at randomization and 13 weeks adjusting for age as fixed effect
1327 and site as a random effect. Missing data will be handled by direct likelihood in this longitudinal
1328 model. This model implicitly adjusts for baseline HbA1c by forcing the treatment groups to have
1329 the same mean value at baseline. Local HbA1c values measured at the site will be included as an
1330 auxiliary variable (analogous to imputing any missing lab values). Regression diagnostics will
1331 be employed as described earlier.

1332 For the binary HbA1c outcomes listed above, risk-adjusted percentages by treatment group will
1333 be computed from a logistic regression model. The logistic regression will adjust for the same
1334 factors mentioned above for the analysis with HbA1c as a continuous factor.

1335 Questionnaires and Other Outcomes

1336 For questionnaires, insulin, weight, and BMI metrics comparisons between treatment arms will
1337 be made using similar methods as described above for the continuous HbA1c analysis.

1338

1339 **8.4.3 Subgroup Analyses**

1340 In exploratory analyses, outcomes for which analyses suggest a treatment group difference will
1341 be assessed separately in various subgroups and for continuous variables according to the
1342 baseline value as defined below. Tests for interaction with treatment group will be performed
1343 and further explored if an interaction will be found in the first place. For continuous variables,
1344 results will be displayed in subgroups based on cutpoints although the analysis will utilize the
1345 variable as continuous. If there is insufficient sample size in a given subgroup, the cutpoints for
1346 continuous measures may be adjusted per the observed distribution of values. Cutpoint selection
1347 for display purposes will be made masked to the outcome data.

- 1348 • Baseline HbA1c
- 1349 • Baseline CGM time spent <70 mg/dL

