199 additionally including factors potentially associated with the outcome for which there is an
200 imbalance between groups (assessed based on clinical judgement reviewing the distributions in the
201 two treatment arms, not on a p-value).
202 • Missing Data: As noted above, all subjects will be included in primary analyses and any missing
203 post-randomization data will be handled using direct likelihood. It is also worth emphasizing that
204 any statistical method for handling missing data makes a number of untestable assumptions. The
205 goal will be to minimize the amount of missing data in this study so that results and conclusions will
206 not be sensitive to which statistical method is used. To that end, sensitivity analyses will be
207 performed to explore whether results are similar for primary analysis when using different
208 methods. The following methods will be applied:
209 ○ Direct likelihood
210 ○ Rubin's multiple imputation
211 ○ Available cases only

212
213
214

215 **2.4. Primary and other CGM Metrics Analyses**

216
217 This study primary outcome is CGM measured % time in range 70-180 mg/dL over 13 weeks.
218
219 Summary statistics (mean \pm SD or median (quartiles)) will be reported for the CGM metrics and for
220 differences from pre-randomization by treatment group.
221 The analyses will be done using direct likelihood. A longitudinal linear regression model will be fit with
222 the metric at baseline and follow-up as the dependent variable. This model will adjust for age as fixed
223 effect and site as a random effect. The analyses will report the point estimate, 95% confidence interval
224 and p-value for the treatment group difference at follow-up. Residual values will be examined for an
225 approximate normal distribution. If residuals are highly skewed, then a transformation or robust
226 statistical method (e.g., non-parametric or M estimation) will be used instead.

227
228

229 **2.5. HbA1c Analyses**

230 Summary statistics (mean \pm SD or n(%)) will be reported for the central lab HbA1c (continuous
231 variable) at randomization and 13-weeks by treatment group. A longitudinal model will be fit using
232 values at randomization and 13 weeks adjusting for age as fixed effect and site as a random effect.
233 Missing data will be handled by direct likelihood in this longitudinal model. This model implicitly
234 adjusts for baseline HbA1c by forcing the treatment groups to have the same mean value at baseline.

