235 Local HbA1c values measured at the site will be included as an auxiliary variable (analogous to
236 imputing any missing lab values). Regression diagnostics will be employed as described earlier.

237 For the binary HbA1c outcomes listed above, risk-adjusted percentages by treatment group will be
238 computed from a logistic regression model. The logistic regression will adjust for the same factors
239 mentioned above for the analysis with HbA1c as a continuous factor.

240

241

242 **2.6. Questionnaires, Insulin, Weight, and BMI Analyses**

243

244 For questionnaires, insulin, weight, and BMI metrics comparisons between treatment arms will be made
245 using similar methods as described above for the primary analysis.

246

247

248 **2.7. Safety Analyses**

249 All enrolled and randomized participants will be included in these analyses and all their safety events up
250 to the 13-week visit will be reported.

251 The circumstances of all reportable cases of the following will be summarized and tabulated by
252 treatment group:

- 253 • Severe hypoglycemia
- 254 • Diabetic ketoacidosis
- 255 • Ketone events defined as a calendar day with ketone level >1.0 mmol/L
- 256 • CGM-measured hypoglycemic events (defined as at least 15 consecutive minutes <54
257 mg/dL)
- 258 • CGM-measured hyperglycemic events (defined as at least 120 consecutive minutes >300
259 mg/dL)
- 260 • Worsening of HbA1c from randomization to 13 weeks by $>0.5\%$
- 261 • Serious adverse events with a possible or greater relationship to a study device (including
262 anticipated and unanticipated adverse device effects)
- 263 • Other serious adverse events not related to a study device
- 264 • Adverse device effects (ADE) that do not meet criteria for SAE

265
266 For the following outcomes, mean \pm SD or summary statistics appropriate to the distribution will be
267 tabulated by treatment group:

- 268 • Number of SH events and SH event rate per 100 person-years
- 269 • Number of DKA events and DKA event rate per 100 person-years
- 270 • Any adverse event rate per 100 person-years

271 If there are at least 10 events across both treatment arms, the numbers will be compared between the two
272 treatment arms using a robust Poisson regression and the percentage of subjects with at least one event
273 will be compared using logistic regression. The regression will adjust for site as random effect. The
274 amount of follow up will be included as an offset covariate to compare the rates.

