
275 The analyses for the two continuous CGM-measured outcomes will parallel those mentioned above for
276 the primary outcome and the worsening in HbA1c will parallel the binary HbA1c models mentioned
277 above.

278 279 **2.8. Device Issues**

280 Reported device issues for each type of study device (e.g., closed-loop system, PLGS system, CGM) by
281 treatment group.

282 283 284 **2.9. Protocol Adherence and Retention**

286 The following tabulations and analyses will be performed by treatment group to assess protocol
287 adherence for the study:

- 288 • Listing of all protocol deviations
- 289 • Tabulation of protocol-specified visits and phone contacts completed in window, out of window and missed for each visit/phone contact
- 290 • Flow chart accounting for all enrolled and randomized participants up to week 13
- 291 • Flow chart of all randomized participants at all scheduled visits and phone contacts to assess visit, and phone completion, and study completion rates
- 292 • Number of and reasons for unscheduled visits and phone calls
- 293 • Number of participants who stopped treatment (CLC or PLGS) and reasons
- 294
- 295
- 296
- 297

298 **2.10. Baseline Descriptive Statistics**

299
300 Baseline demographic and clinical characteristics of the cohort of all randomized participants will be
301 summarized in a table using summary statistics appropriate to the distribution of each variable.
302 Descriptive statistics will be displayed overall and by treatment group.

303
304 Will include:

- 305 • Age at randomization
- 306 • Gender
- 307 • Race/ethnicity
- 308 • Diabetes duration at randomization
- 309 • HbA1c at the end of preceding 6-month RCT
- 310 • BMI at the end of preceding 6-month RCT
- 311
- 312

313 **2.11. Other Tabulations**

314
315 Individual listings for each randomized participant will include the following:

- 316 • Treatment group, age, gender, race/ethnicity, duration, height, weight, and BMI at randomization
- 317
- 318 • Pre-existing medical conditions other than diabetes
- 319 • Medication at enrollment/randomization
- 320 • Baseline glucose metrics
- 321

322 The following tabulations and analyses will be performed by treatment group:

323 • Sensor performance metrics (difference, absolute relative difference, and International
324 Organization for Standardization criteria)

325 • % time CGM data available to the system

326

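### Does the plan leave the primary time-in-range comparison, and the binary HbA1c models, without adjustment for baseline?

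*SAP*

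**What the plan says.** SAP 2.4 (CGM metrics, including the primary outcome) specifies a longitudinal linear regression by direct likelihood, with "the metric at baseline and follow-up as the dependent variable. This model will adjust for age as fixed" effect and site as a random effect. It reports the estimate, 95% interval and p-value for the arm difference at follow-up. Protocol 8.4.2 describes the same model: "fit with the metric at baseline and follow-up as the dependent variable. This model will adjust for" age and site.

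For continuous HbA1c, SAP 2.5 describes a longitudinal model of the randomisation and 13-week values with the same age and site terms, also by direct likelihood. It adds that the model "adjusts for baseline HbA1c by forcing the treatment groups to have the same mean value at baseline". Protocol 8.4.2 says so too: "This model implicitly adjusts for baseline HbA1c by forcing the treatment groups to have" a common baseline mean.

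For binary HbA1c outcomes, SAP 2.5 says that percentages by arm are "computed from a logistic regression model. The logistic regression will adjust for the same factors" as the continuous HbA1c analysis. SAP 2.7 extends the two templates to safety outcomes: the CGM event outcomes follow those for "the primary outcome and the worsening in HbA1c will parallel the binary HbA1c models mentioned" earlier.

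For questionnaires, insulin, weight and BMI, SAP 2.6 compares arms "using similar methods as described above for the primary analysis". Protocol 8.4.2 sends the same outcomes to the continuous HbA1c model.

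Protocol 3.1.1 stratifies randomisation by site and not by baseline time in range, HbA1c or device use, "since these factors will be easier to adjust for in analysis than will site".

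**The concern.** Putting the baseline value on the outcome side does not by itself adjust the follow-up contrast. With complete data, a model with its own baseline mean in each arm returns the raw follow-up difference. A model with one shared baseline mean returns in effect the analysis-of-covariance estimate. SAP 2.4 does not say which is meant, so two analysts could in principle report different estimates and intervals for the primary outcome of the only randomised comparison.

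The logistic models raise a related question. A shared baseline mean is a device of the joint model for baseline and follow-up. It has no counterpart in a logistic regression of 13-week status, where baseline HbA1c has to enter as a covariate, and no covariate list is written out.

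At stake are precision and sensitivity to chance imbalance. Either fit is unbiased over randomisation.

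**Working it through.** **Reading the text**

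1. The CGM and continuous HbA1c models share the same structure: two time points as joint outcomes, age fixed, site random, direct likelihood. Under HbA1c, equal baseline means are presented as a property of the model, not as an extra option.
2. The protocol uses the HbA1c model, and the SAP the primary model, as the template for the same questionnaire, insulin, weight and BMI outcomes. That fits only if the two are regarded as one method.
3. Protocol 3.1.1 gives adjustment in analysis as the reason for not stratifying on baseline time in range or HbA1c.
4. Nothing in either document describes a separate treatment term at baseline.
5. The logistic sentence lists no covariates. It points to an analysis that names age and site and also says it adjusts for baseline HbA1c. Reading it as age and site alone leaves out part of what it points to.

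**What would be lost under the other reading**

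Inputs from the documents: about 100 randomised 1:1 (protocol 8.2; SAP section 2), so n = 50 per arm; 95% intervals (SAP 2.4). Assumptions: SD = 10 percentage points in both arms, correlation r = 0.3 to 0.9, complete data, no age or site terms. The plan has no figure to reproduce, since protocol 8.2 gives no variance estimate and no power.

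- Separate baseline means: SE = SD × √(2/n) = 10 × √(2/50) = 2.0. With t(98) = 1.984 the half-width is 1.984 × 2.0 = 3.97 points.
- Common baseline mean: SE = 2.0 × √(1 − r²).
- A chance baseline difference has SE 2.0, so it exceeds 2 points in a given direction with probability P(Z > 1) = 0.159 (0.317 in either direction). Its mean is then 2.0 × 0.2420/0.1587 = 3.05 points, and the unadjusted estimate is off by r × 3.05.

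| r | SE, common mean | Half-width, common mean | SE ratio, separate/common | Mean error of unadjusted estimate given baseline difference > 2 |
|---|---|---|---|---|
| 0.3 | 1.91 | 3.79 | 1.05 | 0.92 |
| 0.5 | 1.73 | 3.44 | 1.15 | 1.53 |
| 0.7 | 1.43 | 2.83 | 1.40 | 2.14 |
| 0.8 | 1.20 | 2.38 | 1.67 | 2.44 |
| 0.9 | 0.87 | 1.73 | 2.29 | 2.75 |

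Simulation with 20,000 trials per r agrees: mean errors in the last column of 0.90, 1.51, 2.14, 2.41 and 2.77, and within 0.04 of zero after adjustment. Averaged over all trials, both estimators are within 0.03 of the truth.

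A maximum-likelihood fit to one simulated data set (baseline difference 0.104 SD) confirms the mechanism. Separate means gave −0.004 SD, equal to the raw follow-up difference; a common mean gave −0.087 SD, equal to analysis of covariance.

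**Binary HbA1c**

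Assumptions: mean 7.1%, SD 0.9, arms 0.2 apart at 13 weeks, 50 per arm, r = 0.5 to 0.9, 3,000 simulated trials per r.

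- HbA1c below 7.0%: leaving baseline out multiplies the SE of the risk difference by 1.08 to 1.56. A chance baseline difference of 0.2 shifts the risk difference by 4 to 8 percentage points. A difference that large has SE 0.9 × √(2/50) = 0.18, so 0.2/0.18 = 1.11 and a two-sided probability of about 0.27.
- Worsening above 0.5%: the SE ratio is only 1.09 to 1.01 and the shift 4 to 1 points, because baseline is already part of the outcome definition.
- Improvement above 1.0% is sparse. The change has SD 0.9 × √(2(1 − r)). Assuming mean change 0 on CLC and +0.2 on PLGS, expected events in both arms together are about 11, 6, 3 and 0.4 at r = 0.5, 0.7, 0.8 and 0.9. A blanket rule adding a covariate to every binary model would therefore have a cost.

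**The case for a change.** The strongest case for a change is that the omission is a matter of text. Both documents state the common-baseline condition for HbA1c and leave it out for the primary outcome, so a strict reader could infer that the two models differ. SAP 2.6 and 2.7 then carry the silent version to further outcomes. The sensitivity analysis in SAP 2.3.2 adds covariates only where imbalance is judged present. It does not define the primary estimate and recovers no precision when the arms look balanced. Exploratory status does not make an estimate reproducible, and the repair would be a sentence or two.

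Part of this stands. The sentence is absent from SAP 2.4, a logistic model needs baseline HbA1c as an explicit term, and SAP 2.3.2 is only a partial safeguard. What does not stand is the step from a missing sentence to a real risk of an unadjusted analysis. The inference that the models differ is hard to hold beside their identical form, their interchangeable use as templates and the reasoning in protocol 3.1.1. For the logistic models, the natural reading of the back-reference already includes baseline HbA1c.

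**Conclusion.** No change to the plan is needed. The primary CGM section leaves unsaid a property that the documents state for a model of the same form, and the surrounding text points one way. An analyst following the plan would constrain the baseline means and put baseline HbA1c in the logistic models; on that reading no precision is lost.

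If separate baseline means were fitted instead, the SE would be 1.05 to 2.29 times larger and the half-width 4.0 points instead of 3.8 to 1.7. That size rests on an assumed SD of 10 points and on r = 0.3 to 0.9, equal in both arms although one arm changes device. The largest ratios need r of 0.8 or 0.9, which no document supports.

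There is no bias over randomisation. The error-control argument has no hold either, since all Objective 1 comparisons are declared exploratory, without multiplicity adjustment or a power claim. Repeating the HbA1c sentence in SAP 2.4 would do no harm, but it would only write down what the plan already implies.
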